5.2 Analysis methods

The main analysis (primary outcome) will compare TNFi and IL-6i in terms of change of LVM from baseline to follow-up after an exercise intervention of 12 weeks (Shell Table 2 and Shell Figure 2). We will assess this superiority analysis based on the ITT population. Change from baseline will be calculated as the value collected after 12 weeks minus the initial value; An increase in LVM indicates cardiac adaptions to exercise. To analyse the change from baseline, we will use an ANCOVA model, and report the least squares means with standard errors. For the main analyses, missing values will be replaced by a simplistic non-responder imputation technique (i.e., baseline observation carried forward). The model will include the level at baseline as a covariate, and fixed effect factors for sex, group (Exercise vs Management as usual), and concomitant bDMARD use (TNFi vs. IL-6i). For the purpose of sensitivity analysis, we will also attempt to account for baseline values and previous bDMARDs treatment (number of drugs used prior to the treatment at enrollment).

$$\Delta LVM = \text{Group} + \text{sex} + \text{bDMARD} + \text{Group} * \text{bDMARD} + f(LVM_{\text{baseline}})$$

The primary analysis will be conducted following week 12 based on the change from baseline variable (e.g., ΔLVM). We will report the difference between the randomised groups with a 95% CI and the associated P-value, which tests the null hypothesis of no difference between the groups.

We will claim superiority if the calculated 95% CI of the estimated group difference in the change from baseline does not include 0 in the ITT population. To ensure the validity of our model, several assumptions will be assessed. These include checking for normal distribution of the residuals and assessing the homogeneity of the variance by examining the standardized residuals in relation to the predicted values. In cases where variables do not meet the model assumptions, appropriate transformations will be applied to address the issue. However, if no suitable transformation is found, the results will be reported in terms of median change along with interquartile ranges. In such instances, suitable non-parametric statistical tests will be employed for analysis and testing.

Analysis of secondary outcomes will follow the same method as described above. Results will be presented in Shell table 2.

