1.3 Aim and objectives

Primary aim:

To investigate if the effects of exercise training on cardiac structure and function in RA patients vary depending on the concomitant treatment with either TNFi or IL-6i.

Primary objective:

To evaluate whether concomitant use of one of the two different bDMARDs impact the effect of 12 weeks of regular supervised exercise, relative to treatment as usual, on changes in left ventricular mass (LVM, measured in grams [g]) measured by cardiac magnetic resonance imaging (CMR) from baseline to week 12, in RA patients in stable treatment with either a TNF- or IL6-inhibitor.

Key secondary objectives:

To explore, in patients with RA in stable treatment with either a TNF- or IL-6-inhibitor, whether concomitant use of one of the two different biologics impact the effect of 12 weeks of regular supervised exercise, relative to treatment as usual, after 12 weeks on changes in:

1. Left ventricular stroke volume
2. Left ventricular end diastolic volume
3. Relative VO₂peak
4. Disease Activity Score-28 for rheumatoid arthritis based on the erythrocyte sedimentation rate

Other secondary objectives:

Further to explore the effect of concomitant use of one of the two different biologics impact the effect of 12 weeks of regular supervised exercise, relative to treatment as usual, after 12 weeks on changes in:

- LVM/body surface area
- Left ventricular global longitudinal strain
- Left ventricular ejection fraction
- Left ventricular end-systolic volume
- Absolute VO₂peak
- Total lean mass
- Total fat mass
- Resting heart rate

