1.4 Hypothesis

We hypothesise that pharmacological inhibition of IL-6 (unlike TNFi) impairs exercise-induced changes in LVM. The null hypotheses are that there is no difference between the exercise and control group, and this apparent null effect cannot be effect modified by the concomitant choice of biological agent (IL-6i vs TNFi).

2 Methods

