2.1 Trial design

All procedures and detailed information about the design, assessments, inclusion and exclusion criteria and interventions has been published elsewhere (11). Briefly, this study is a single-centre, randomised, parallel group, investigator-blinded trial with a primary endpoint of changes in LVM after 12 weeks measured by cMRI. The study was designed to include 80 participants: After patients signed the informed consent form, participants were randomised to either exercise (experimental intervention) or no exercise (control comparator).

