2.4 Framework

The study was designed as a superiority trial, testing the effect of exercise compared to control, and explore the possible ‘effect modifying impact’ of IL6i (11) as a contextual factor. Statistical analyses of RCTs respecting the intention-to-treat population yield a causally valid estimate of the average treatment effect, which is the contrast between the outcomes in the two randomised treatment groups commonly accompanied by a confidence interval. The primary objective of the RABEX Trial however is to examine whether any observed treatment effect varies across patient subgroups; i.e., whether the treatment effect is modified by the value of a variable assessed at baseline (12).

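### The primary objective is whether the biologic modifies the exercise effect, but the only success rule concerns exercise versus control, and no sentence makes the Group*bDMARD test decisive

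*SAP*

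**What the plan says.** The objective is stated twice as effect modification. Section 1.3 sets out "To evaluate whether concomitant use of one of the two different bDMARDs impact the effect of 12 weeks of regular supervised exercise", relative to usual treatment, on change in left ventricular mass (LVM). Section 2.4 ends with "The primary objective of the RABEX Trial however is to examine whether any observed treatment effect varies across patient subgroups".

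Other passages put exercise versus control beside it or ahead of it. Section 1.4 says "The null hypotheses are that there is no difference between the exercise and control group, and this apparent null effect cannot be effect modified", with the biologic as the modifier, which is two nulls without a ranking. Section 2.4 opens with "The study was designed as a superiority trial, testing the effect of exercise compared to control, and explore the possible" modifying role of IL-6 inhibition.

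The analysis section fits one ANCOVA with baseline LVM, the Group*bDMARD product and "fixed effect factors for sex, group (Exercise vs Management as usual), and concomitant bDMARD use (TNFi vs. IL-6i"). It then states "We will report the difference between the randomised groups with a 95% CI and the associated P-value", and the success rule for the ITT analysis follows: "We will claim superiority if the calculated 95% CI of the estimated group difference in the change from baseline does not include 0". Section 2.1 confirms which factor is randomised: "participants were randomised to either exercise (experimental intervention) or no exercise (control comparator").

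Shell Tables 2 and 3 have a difference column headed with a 95% CI and an Interaction column headed without one. Section 3.1 sets a two-sided 0.05 level throughout. It orders the secondary objectives for gatekeeping and stops at the first outcome without a significant difference, but does not say which difference. Section 5.2 sends secondary outcomes through the same method as the primary.

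**The concern.** The decision rule tests a different hypothesis from the one the SAP calls primary. An exercise-versus-control interval that excludes 0 can reflect a real exercise effect and still say nothing about whether IL-6 inhibition blunts it. Nothing in the plan stops such a result from being presented as the answer to the primary objective.

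The gap carries into the secondary outcomes. Section 1.3 words them as modification questions, but the stopping criterion in 3.1 can be read as exercise versus control. The step at which the sequence stops therefore depends on a choice the plan leaves open until the results are available.

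A third contrast adds to the ambiguity. Section 2.3 powers TNFi against IL-6i among exercisers only, and the opening of 5.2 loosely describes the same comparison. It uses no controls, although the objective is defined relative to usual treatment.

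**Working it through.** **Inputs.** From section 2.3: difference 12 g, SD 12.3 g, two-sided 5% level, 80% power, 16 per group needed, 20 per stratum-by-group cell planned (80 in total). Assumed here: SD 12.3 g in all four cells, controls change by 0 g, covariates explain 0% or 30% of the variance, and the group difference is averaged over the two drugs.

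**1. The plan's own figure.** By the normal approximation, n per group = 2 × (12.3 × (1.960 + 0.842) / 12)² = 16.49, against the stated 16. The exact t-test needs 18. Power at 16 per group is 78.8% (normal) or 76.1% (exact t); at 20 it is 85.2% (exact t). The figure reproduces closely, but only for TNFi versus IL-6i among exercisers.

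**2. Standard errors of the two candidate tests, n per cell.**
- Exercise minus control, averaged over drugs: SD/√n. At n = 20, 12.3/√20 = 2.75 g; at n = 16, 3.08 g.
- Interaction (difference between the two exercise effects): 2 × SD/√n. At n = 20, 5.50 g; at n = 16, 6.15 g.

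**3. How often each test is significant.** Noncentral t, 4n − 6 degrees of freedom, two-sided 0.05, n = 20, no covariate gain. Disagreement comes from 20,000 simulated trials per scenario, analysed by ANCOVA with group, bDMARD, their product, sex and baseline.

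| Exercise effect, TNFi / IL-6i (g) | Average effect (g) | Size of interaction (g) | 5.2 rule met | Interaction significant | Tests disagree |
|---|---|---|---|---|---|
| 12 / 12 | 12 | 0 | 99.1% | 5.0% | 94.2% |
| 12 / 6 | 9 | 6 | 89.8% | 19.0% | 74.2% |
| 12 / 0 | 6 | 12 | 57.7% | 57.7% | 48.8% |

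In the last row the two rejection rates are equal because 6/2.75 = 12/5.50 = 2.18. The disagreement splits almost evenly: 24.8% with only the group test significant and 24.0% with only the interaction significant.

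**4. Range.** Each entry is rule met / interaction significant / disagree.

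| Setting | 12 / 12 | 12 / 6 | 12 / 0 |
|---|---|---|---|
| n = 16, covariates 0% | 97.0 / 5.0 / 92.0% | 82.1 / 16.0 / 71.0% | 48.4 / 48.4 / 48.9% |
| n = 20, covariates 30% | 99.9 / 5.0 / 94.9% | 97.1 / 25.1 / 73.5% | 73.0 / 73.0 / 39.4% |
| n = 16, covariates 30% | 99.6 / 5.0 / 94.6% | 93.1 / 20.9 / 75.1% | 63.1 / 63.1 / 46.6% |

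In the 30% rows, disagreement is p(1 − q) + q(1 − p), with p and q the two rejection rates. This treats the two estimates as independent, as in a balanced design.

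**5. Power of the interaction test.** For a 12 g interaction it is 57.7% at 20 per cell and 48.4% at 16. By the normal approximation, the difference detectable with 80% power is 5.50 × 2.802 = 15.4 g at 20 per cell and 6.15 × 2.802 = 17.2 g at 16. Reaching 80% power for 12 g needs about 34 per cell, or 136 patients.

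**The case against.** The interaction is more firmly planned than the success rule suggests. Section 1.3 states the objective clearly, and the last sentence of 2.4 corrects its opening. The product term is in the prespecified model, the tables have a column for it and 3.1 fixes the level. On this view only a linking sentence is missing. That describes the gap fairly, but the missing sentence is the one that decides the primary conclusion, and the rule that is written points elsewhere.

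The superiority wording can also be traced back to the opening of 5.2, which compares TNFi with IL-6i. The disagreement figures above would not apply on that reading. But the SAP defines group as exercise versus usual management and refers to randomised groups, and a comparison among exercisers is still not the interaction test.

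Disagreement is not error. With 12 g under both drugs, a significant exercise effect and a non-significant interaction are both correct. Harm arises only if one result is reported as the other. This stands, and the percentages should be read that way.

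The power figures assume complete outcomes, whereas 5.2 carries the baseline value forward for missing ones. If 4 of 20 per cell were set to zero change, interaction power for 12 g would be about 47% instead of 58%. That makes the power less favourable still.

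Finally, an ordered pair of tests would also remove the ambiguity, since 1.4 states two nulls. It would, but a single primary interaction test follows most directly from the objective the SAP itself calls primary.

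**Conclusion.** The concern holds and should be settled before the primary result is interpreted. The SAP's objective is effect modification. Its only success rule is best read as exercise versus control, and no passage ranks the two or gives the interaction a deciding role. This conclusion rests on the text and does not depend on the calculations.

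The calculations show that the choice matters. Over 16 to 20 per cell, with covariates explaining 0 to 30% of the variance, the two tests give different answers in 92–95% of trials with no blunting, 71–75% with half blunting and 39–49% with full blunting. These figures are scenario-based and rest on a common SD of 12.3 g, no change in controls and no missing outcomes. The 80% power in 2.3 belongs to a third contrast and does not describe the test of the primary objective.

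**What to change.** - **Section 5.2:** name (exercise minus control under IL-6i) minus (exercise minus control under TNFi), on change in LVM in grams, as the single primary test, with its 95% CI and P value. Attach the decision rule to it.
- **Section 3.1:** state that the same contrast drives every gatekeeping step.
- **Supportive results:** report the overall and within-drug exercise-versus-control differences as supportive, and label any superiority claim as exercise versus control only.
- **Consistency:** align 1.4, 2.4 and the opening of 5.2. Give an estimate with 95% CI in the Interaction column of Shell Tables 2 and 3.
- **Section 2.3:** say that the calculation concerns two cells of exercisers (exact power about 76% at 16 and 85% at 20 per group). Add that it is not the power of the interaction test. For 12 g that is about 58% at 20 per cell and 48% at 16 under the same SD, or about 73% and 63% if covariates explain 30% of the variance.

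The change is to wording only. The term is already in the model, and no new data or enrolment is needed. The cost is a less favourable power figure for the primary test. Timing also matters: section 2.6 expected primary data by mid October 2023, the version 1.1 changes are dated November 2023, and the SAP does not show whether unblinding had occurred. If it had, record the change as a dated clarification.

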5.3 Sensitivity analysis

We will conduct sensitivity analyses for both primary and secondary outcomes. Initially, we will reiterate the primary analysis, but this time employing the Per Protocol (PP) population instead of the Intention-to-Treat (ITT) population.

$$\Delta\text{Variable} = \text{Group} + \text{sex} + \text{bDMARD} + \text{Group} * \text{bDMARD} + f(\text{Variable}_{\text{baseline}}) + \text{Previous_bDMARD} + \text{Radiagnosis_years}$$

Results will be presented as illustrated in Shell table 3.

5.4 Missing data

The database will undergo a thorough examination of all variables, including derived ones, to detect any missing values, outliers, or inconsistencies. Outliers will be identified by visually inspecting the maximum and minimum values, comparing them to the values recorded in the eCRF, and noting any significantly high or low values. If any outliers are found to be incorrect, they will be corrected if possible. Otherwise, they will be treated as missing data. Since the trial is being monitored by the external Good Clinical Practice Unit at Copenhagen University Hospitals, we anticipate minimal occurrence of faulty data points. The monitor has conducted pre-trial site visits and regular inspections throughout the trial, ensuring compliance with trial procedures, safety assessments, as well as data recording and verification.

5.5 Harms

All participants will undergo evaluations of adverse events (AEs), adverse reactions (ARs), serious adverse events (SAEs), serious adverse reactions (SARs), and suspected unsuspected serious adverse reactions (SUSARs). The frequency (and proportion) of participants encountering AEs and SAEs will be reported for each treatment group, classified according to their severity. Each participant's record will only show the highest level of severity experienced for each type of event

or reaction. No formal statistical analysis will be conducted. If needed, the classification categories for events and reactions will be expanded (Shell appendix 5).

5.6 Statistical software

Statistical analysis will be done in R (version 4.2.2 or more updated version). Figures will be done in either R or GraphPad Prism (most updated version available).

5.7 Changes to protocol

Inclusion criteria: DAS28-ESR was changed from 2.8 to 3.2 on December 17, 2021, to increase enrollment. A DAS28-ESR score of 3.2 as well as 2.8 suggests low disease activity.

6 Tables and figures

Shell Table 1. Baseline Characteristics		Exercise	Control	Overall
Demographics				
Female/Male, n	Total			
	TNF α			
	IL-6 α			
Age, years	Total			
	TNF α			
	IL-6 α			
BMI, kg/m 2	Total			
	TNF α			
	IL-6 α			
RA characteristics				
Duration of RA, years	Total			
	TNF α			
	IL-6 α			
DAS28-ESR	Total			
	TNF α			
	IL-6 α			
HAQ-DI	Total			
	TNF α			
	IL-6 α			
Sero-positive RA, n (%)	Total			
	TNF α			
	IL-6 α			
SR,mm	Total			
	TNF α			
	IL-6 α			
IL-6, pg/ml	Total			
	TNF α			
	IL-6 α			
Cardiac Measures				
LVM, g	Total			
	TNF α			
	IL-6 α			
LVSV, ml	Total			
	TNF α			
	IL-6 α			

LVEDV, ml	Total			
	TNF _i			
	IL-6 _i			
LVM/BSA, g/m ²	Total			
	TNF _i			
	IL-6 _i			
LV GLS (%)	Total			
	TNF _i			
	IL-6 _i			
LVEF, %	Total			
	TNF _i			
	IL-6 _i			
LVESV, ml	Total			
	TNF _i			
	IL-6 _i			
Resting HR, bpm	Total			
	TNF _i			
	IL-6 _i			
SBP, mmHg	Total			
	TNF _i			
	IL-6 _i			
DBP, mmHg	Total			
	TNF _i			
	IL-6 _i			
Metabolic measures				
Total lean mass, kg	Total			
	TNF _i			
	IL-6 _i			
Total fat mass, kg	Total			
	TNF _i			
	IL-6 _i			
Fitness measures				
Absolute Vo ₂ peak, ml/min	Total			
	TNF _i			
	IL-6 _i			
Relative Vo ₂ peak, ml/min/kg	Total			
	TNF _i			
	IL-6 _i			

Shell Table 1. Baseline Characteristics. Values are depicted in means (SD) or number and percentage. BMI, body mass index; RA, rheumatoid arthritis; DAS28-ESR, Disease Activity Score-28 for rheumatoid arthritis with erythrocyte sedimentation rate; HAQ-DI, health assessment questionnaire disability index; SR, sedimentation rate; IL-6, interleukin-6; bDMARD, biological disease modifying anti rheumatic drug; LVM, left ventricular mass; LVSV; left ventricular stroke volume; LVEDV; left ventricular end-diastolic volume; BSA, body surface area; GLS, global longitudinal strain; LVEF, left ventricular ejection fraction; LVESV, left ventricular end-systolic volume; HR, heart rate; SBP, systolic blood pressure; DBP, diastolic blood pressure

Shell Table 2. Outcomes after 12 weeks in ITT population		Exercise	Control	Difference between groups (95% CI)	Interaction
Δ LVM, g	Total				
	TNF _i				
	IL-6 _i				
Key secondary outcomes					
Δ LVSV, ml	Total				
	TNF _i				
	IL-6 _i				
Δ LVEDV, ml	Total				
	TNF _i				
	IL-6 _i				
Δ /Relative Vo ₂ peak, ml/min	Total				
	TNF _i				
	IL-6 _i				
Δ DAS28-ESR	Total				
	TNF _i				

	IL-6i			
Other secondary outcomes				
Δ LVM/BSA, g/m ²	Total			
	TNFi			
	IL-6i			
Δ LV GLS (%)				
Δ LVEF, %	Total			
	TNFi			
	IL-6i			
Δ LVESV	Total			
	TNFi			
	IL-6i			
Δ Absolute Vo ₂ peak, ml/min	Total			
	TNFi			
	IL-6i			
Δ Total lean mass, kg	Total			
	TNFi			
	IL-6i			
Δ Total fat mass, kg	Total			
	TNFi			
	IL-6i			
Δ Resting HR, bpm	Total			
	TNFi			
	IL-6i			

Shell Table 2. Values are depicted in least square means [95% CI]. LVM, left ventricular mass; LVSV; left ventricular stroke volume; LVEDV; left ventricular end-diastolic volume; DAS28-ESR, Disease Activity Score-28 for rheumatoid arthritis with erythrocyte sedimentation rate; BSA, body surface area; GLS, global longitudinal strain; LVEF, left ventricular ejection fraction; LVESV, left ventricular end-systolic volume; HR, heart rate

Shell Table 3. Outcomes after 12 weeks in PP population		Exercise	Control	Difference between groups (95% CI)	Interaction
Δ LVM, g	Total				
	TNFi				
	IL-6i				
Key secondary outcomes					
Δ LVSV, ml	Total				
	TNFi				
	IL-6i				
Δ LVEDV, ml	Total				
	TNFi				
	IL-6i				
Δ /Relative Vo ₂ peak, ml/min	Total				
	TNFi				
	IL-6i				
Δ DAS28-ESR	Total				
	TNFi				
	IL-6i				
Other secondary outcomes					
Δ LVM/BSA, g/m ²	Total				
	TNFi				
	IL-6i				
Δ LV GLS (%)	Total				
	TNFi				
	IL-6i				
Δ LVEF, %	Total				
	TNFi				
	IL-6i				
Δ LVESV	Total				
	TNFi				
	IL-6i				

Δ Absolute Vo ₂ peak, ml/min	Total				
	TNF _i				
	IL-6 _i				
Δ Total lean mass, kg	Total				
	TNF _i				
	IL-6 _i				
Δ Total fat mass, kg	Total				
	TNF _i				
	IL-6 _i				
Δ Resting HR, bpm	Total				
	TNF _i				
	IL-6 _i				

Shell Table 3. Values are depicted in least square means [95% CI]. LVM, left ventricular mass; LVSV; left ventricular stroke volume; LVEDV; left ventricular end-diastolic volume; DAS28-ESR, Disease Activity Score-28 for rheumatoid arthritis with erythrocyte sedimentation rate; BSA, body surface area; LVEF, left ventricular ejection fraction; LVESV, left ventricular end-systolic volume; HR, heart rate

Shell Appendix 1. Secondary outcomes documented in Clinical trials that are not covered in the present statistical analysis plan.

Clinical trials secondary outcome number	Outcome
1	Visceral adipose tissue mass
3	Left atrial end-diastolic volume
6	E/A
7	E/ \dot{e}
8	Left atrial end-systolic volume
9	Left atrial volume index
10	Interventricular septum thickness
11	Left ventricular posterior wall thickness
12	Aortic and pulmonary disensibility and pulse wave velocity
13	Subcutaneous, visceral and epicardial adipose tissue
14	Intramyocardial triglyceride content
16	Dynamic spirometry
17	Whole body plethysmography
18	Diffusion capacity
20	Oral glucose tolerance test
23	Blood sample (cholesterol, LDL, HDL)
24	Blood sample (triglycerides)
25	RA disease specific outcomes 1 (66/68 tender and swollen joint)
26	RA disease specific outcomes 2 (VAS)
28	RA disease specific outcomes 4 (SF-36)
30	RA disease specific outcomes 6 (CDAI)
31	RA disease specific outcomes 7 (ACR 20/50/70)
32	RA disease specific outcomes 8 (EULAR none/good/moderate)

Shell Appendix 1. E/A, early (E) to late (A) ventricular filling velocities; E/ \dot{e} , early mitral inflow velocity and mitral annular early diastolic velocity; LDL, low density lipoprotein; HDL, high density lipoprotein; VAS, visual analog scale; SF, short form; CDAI, clinical disease activity index; ACR, american college of rheumatology; EULAR, european league against rheumatism

Shell appendix 2. Self-reported diet, self-reported physical activity prior to enrollment, and measured free-living physical activity		Exercise	Control	Difference
Diet				
Energy intake (kcal/day)	Total			
	TNF _i			
	IL-6 _i			
Physical Activity				
Self-reported weekly exercise sessions at baseline, n	Total			
	TNF _i			
	IL-6 _i			
Free living physical activity				
Valid days, n	Total			
	TNF _i			
	IL-6 _i			
Wear time, h/day	Total			
	TNF _i			

	IL-6i			
Total physical activity, counts/min per day	Total			
	TNFi			
	IL-6i			
MVPA, min/day	Total			
	TNFi			
	IL-6i			
Sedentary, min/day	Total			
	TNFi			
	IL-6i			
Walking, min/day	Total			
	TNFi			
	IL-6i			

Shell appendix 2. Values are presented as mean (SD) or median and interquartile range. h, hour; MVPA, moderate and vigorous physical activity

Shell appendix 3. Adherence to exercise and bDMARDs		Exercise	Control	Difference in groups (95% CI)
Exercise intervention				
Total sessions attended, n	Total		-	
	TNFi		-	
	IL-6i		-	
Time in heart rate zone 1 (<70% HR max), min	Total		-	
	TNFi		-	
	IL-6i		-	
Time in heart rate zone 2 (70-74% HR max), min	Total		-	
	TNFi		-	
	IL-6i		-	
Time in heart rate zone 3 (75-79% HR max), min	Total		-	
	TNFi		-	
	IL-6i		-	
Time in heart rate zone 4 (80-84% HR max), min	Total		-	
	TNFi		-	
	IL-6i		-	
Time in heart rate zone 5 (≥85% HR max), min	Total		-	
	TNFi		-	
	IL-6i		-	
Watt outputs during HIIT intervals, watt	Total		-	
	TNFi		-	
	IL-6i		-	
Average BORG	Total		-	
	TNFi		-	
	IL-6i		-	
bDMARD treatment				
bDMARD compliance, %	Total			
	TNFi			
	IL-6i			

Shell appendix 3. Values are presented as mean (SD) or median and interquartile range. HR, heart rate; bDMARD, biological disease modifying antirheumatic drug; TNFi, tumour necrosis factor inhibitor; IL-6i, interleukin-6 inhibitor; FU, follow-up

Shell Appendix 4. Supplemental baseline characteristics		Exercise	Control	Overall
Concomitant medications				
Oral steroids, n(%)	Total			
	TNFi			
	IL-6i			
csDMARD, n(%)	Total			
	TNFi			
	IL-6i			
Betablocker, n(%)	Total			

[figure not shown]
	TNFi			
	IL-6i			
Other antihypertensive, n(%)	Total			
	TNFi			
	IL-6i			
NSAIDs, n(%)	Total			
	TNFi			
	IL-6i			
Statins, n(%)	Total			
	TNFi			
	IL-6i			
Comorbidites				
Muskoskeletal disease, n (%)	Total			
	TNFi			
	IL-6i			
Cardiovascular disease, n (%)	Total			
	TNFi			
	IL-6i			
Pulmonary disease, n (%)	Total			
	TNFi			
	IL-6i			
Prior bDMARD use	Total	0: n(%)		
		1: n(%)		
		≥2: n(%)		
	TNFi	0: n(%)		
		1: n(%)		
		≥2: n(%)		
	IL-6i	0: n(%)		
		1: n(%)		
		≥2: n(%)		

Shell Appendix 4. Values are mean (SD) unless noted otherwise. csDMARD, conventional synthetic disease modifying antirheumatic drugs; NSAIDs, non-steroid anti-inflammatory drug..

[figure not shown]
Shell appendix 5. Adverse events		Exercise	Control
SAE, no. (%)	Total		
	TNFi		
	IL-6i		
All AE			
Muskuoloskeletal pain and injuries			
Lower extremities, no. (%)	Total		
	TNFi		
	IL-6i		
Upper extremities, no. (%)	Total		
	TNFi		
	IL-6i		
Back pain, no. (%)	Total		
	TNFi		
	IL-6i		
Other, no. (%)	Total		
	TNFi		
	IL-6i		
Infections			
Bacterial infections, no. (%)	Total		
	TNFi		
	IL-6i		
Viral infections, no. (%)	Total		
	TNFi		
	IL-6i		
Other, no. (%)	Total		
	TNFi		
	IL-6i		
Cardiovascular disorders			
Pectoral Angina, no. (%)	Total		
	TNFi		
	IL-6i		
Arrythmia, no. (%)	Total		

	TNFi	
	IL-6i	
Other, no. (%)	Total	
	TNFi	
	IL-6i	
	Neurological disorders	
Headaches, no. (%)	Total	
	TNFi	
	IL-6i	
Dizziness, no. (%)	Total	
	TNFi	
	IL-6i	
Other, no. (%)	Total	
	TNFi	
	IL-6i	

Shell appendix 5. Values are number and percentage (%) of participants with AE for each group. SAE; serious adverse event, AE; adverse event.

Shell Figure 1. Flowchart. BL, baseline; FU, Follow-up

